In Iraq, mental health services incorporation into oncology care remains substantially inadequate. Mental health professionals are scarce in most oncology centers, and psychological screening is not routinely performed during cancer diagnosis or follow-up. Cultural stigma surrounding mental illness may also contribute to the underreporting of emotional symptoms and poor help-seeking behavior. According to a 2023 WHO-EMRO report, less than 15% of patients in Iraq received psychological support, even though studies consistently demonstrate a high rate of undiagnosed mood disorders in this group of patients (12).

The present study aims to examine the psychosocial, clinical, and economic correlations of depression, anxiety, and stress among breast cancer patients in Al-Anbar city. Applying a multidimensional analytic approach, including multivariate linear and logistic regression, ROC analysis, and path modeling. This study explains how individual, emotional, and treatment-related factors interact to shape mental health outcomes. The findings are intended to guide more culturally sensitive and systemically integrated psychological interventions for cancer patients in Iraq and the region.

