### **2-3 Sample Size Calculation**

The sample size was calculated using the standard formula for cross-sectional studies, with the following parameters: a 95% confidence level, a 5% margin of error, and an expected prevalence of psychological distress of 50% to yield the largest possible sample size. Based on these assumptions, the minimum required sample size was estimated to be 384 participants. To enhance the statistical power and compensate for potential non-response or incomplete data, a larger sample was targeted. Consequently, a total of 500 breast cancer patients were enrolled in the final analysis, exceeding the minimum requirement.

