## **2-6 Data Analysis**

Data was analyzed using IBM SPSS Statistics version 26. Descriptive statistics (mean, standard deviation, frequency, and percentage) were used to summarize demographic and clinical variables. The Kolmogorov-Smirnov test was applied to assess the normality of continuous variables, and due to non-normal distribution, non-parametric tests were used.

Bivariate analyses included Spearman's correlation coefficient to evaluate associations between psychological outcomes (depression, anxiety, stress) and continuous predictors such as sleep quality, cost, and number of children. The Kruskal-Wallis H test was employed to examine differences in distress levels across cancer stages.

Categorical associations were evaluated using Pearson's Chi-square test. Binary logistic regression analysis was conducted to identify predictors of severe anxiety. Additionally, multivariate linear regression models were constructed for each psychological outcome (PHQ-9, GAD-7, stress), and multicollinearity was assessed using the Variance Inflation Factor(VIF).

Receiver Operating Characteristic (ROC) curve analysis was used to assess the predictive accuracy of stress scores for severe anxiety, with Area Under the Curve (AUC) interpreted based on conventional thresholds. Conceptual path modeling was used to explore potential indirect relationships between stress and anxiety, mediated by sleep disturbance and impaired daily performance.

All tests were two-tailed, and a p-value of less than 0.05 was considered statistically significant.

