**Table 5:** Binary Logistic Regression – Predicting Severe Anxiety

Predictor	Odds Ratio (OR)	95% CI	P-value
Depression (PHQ-9)	1.32	1.18 – 1.56	<0.001

Anger	1.27	1.11 – 1.49	0.002
Stress Level	1.14	1.03 – 1.35	0.017
Psychological Support	0.54	0.33 – 0.91	0.021
Cancer Stage	0.61	0.33 – 0.87	0.049

[figure not shown]
Binary logistic regression (**Table 5**) showed that depression, anger, and stress significantly increased the odds of severe anxiety, while psychological support and advanced cancer stage were protective. The corrected model (**Table 6**) confirmed these associations.

**Table 6.** Logistic Regression Predicting Severe Anxiety (Corrected Model)

Predictor	Coef. ( $\beta$ )	Std. Error	z-value	p-value	95% CI (Lower – Upper)
PHQ9_Total	0.42	0.06	6.92	<0.001	0.30 – 0.53
Anger	2.08	0.48	4.36	<0.001	1.14 – 3.02
Psych Support	-0.18	0.34	-0.52	0.606	-0.84 – 0.49
Cancer Stage	0.92	0.29	3.20	0.0014	0.36 – 1.48

[figure not shown]
This table presents the corrected logistic regression model for predicting severe anxiety. PHQ9\_Total and anger were significant positive predictors, while psychological support did not show a significant protective effect in the adjusted model.

**Figure 2.** ROC Curve for stress predicting severe anxiety.

The ROC curve (**Figure 2**) illustrates the predictive value of stress scores for severe anxiety, with an AUC of 0.74 ( $p < 0.001$ ), indicating fair discriminative accuracy.

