Furthermore, Kruskal-Wallis analysis confirmed significant differences in mean ranks of depression, anxiety, and stress across cancer stages ( $H = 14.76$  to  $31.09$ ,  $p < 0.01$ ). These findings are supported by evidence from Iran and neighboring countries, where patients with stage III and IV breast cancer reported higher rates of emotional distress compared to the early stages of the disease (14). The increased psychological vulnerability in advanced stages underscores the need for stage-specific psychosocial interventions in cancer care protocols

Interestingly, total treatment cost showed a weak but statistically significant inverse correlation with psychological distress variables (e.g., PHQ-9\_Total:  $r = -0.11$ ,  $p = 0.017$ ). Although initially counterintuitive, this finding may reflect a perceived sense of security or access to higher-quality care among patients with greater financial capacity. Similar interpretations were reported in recent findings from Turkey, where patients with access to private sector services and higher financial resources exhibited lower levels of psychological distress despite elevated treatment costs, suggesting that financial ability may buffer emotional burden through enhanced control and perceived care quality (17).

As for psychological support, logistic regression models from this study suggested a protective effect ( $OR = 0.54$ ), though this was not statistically significant in the adjusted model ( $p = 0.606$ ). The lack of significance may be attributed to limited availability or underutilization of structured psychological services in the region, a challenge frequently reported in Iraq and across low-resource Middle Eastern settings. (18,19). Nonetheless, the direction of effect emphasizes the urgent need to integrate psychosocial support into routine oncology care.

Among all predictors examined, depression (PHQ9\_Total) and anger emerged as the strongest independent predictors of severe anxiety in both logistic and linear regression models ( $\beta = 0.42$  and  $2.08$ , respectively,  $p < 0.001$ ). These findings support prior research indicating that depressive symptomatology often precedes or co-occurs with anxiety in cancer patients, especially when emotional regulation is compromised (11)

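### No primary outcome or contrast is named and every test is judged at an unadjusted 0.05, so six results with p from 0.017 to 0.049 should be labelled exploratory

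*Combined protocol and SAP*

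**What the plan says.** The Introduction states the aim without ranking the outcomes: "The present study aims to examine the psychosocial, clinical, and economic correlations of depression, anxiety, and stress among breast cancer patients in Al-Anbar city". Section 2-6 then lists Spearman, Kruskal-Wallis, chi-square, linear and logistic analyses of these outcomes and closes with the only decision rule: "All tests were two-tailed, and a p-value of less than 0.05 was considered statistically significant". Exploration is mentioned only for the path model.

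Section 2-3 does not supply a primary test. It sizes the study for the precision of one proportion, using "a 95% confidence level, a 5% margin of error, and an expected prevalence of psychological distress of 50" per cent, and concludes that "the minimum required sample size was estimated to be 384 participants".

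Two statements rest on results in the weak range:
- Results, on Table 5: "depression, anger, and stress significantly increased the odds of severe anxiety, while psychological support and advanced cancer stage were protective".
- Discussion, on cost: "total treatment cost showed a weak but statistically significant inverse correlation with psychological distress variables" (PHQ-9: r = -0.11, p = 0.017).

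**The concern.** With three co-equal outcomes, many predictors and a flat 0.05, some p-values just under 0.05 are expected by chance. The rule treats a result at p = 0.045 the same as one at p < 0.001, so a reader cannot tell solid associations from fragile ones. Interpretation is then built on the fragile ones. The Discussion offers a financial-security explanation for the cost correlation, and it uses the direction of the support odds ratio to argue for services.

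**Working it through.** **1. The plan's own figure.** n = z² p(1 − p)/d² = 1.96² × 0.25/0.05² = 384.2, which agrees with the stated 384. It concerns one prevalence and gives no primary hypothesis.

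**2. Number of tests.** Table 4 has 6 (depression) + 6 (anxiety) + 5 (stress) = 17. Table 5 has 5. Table 2 has 9 outcome-by-predictor correlations (sleep difficulty, sleep satisfaction and cost, each against three outcomes).

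**3. Family-wise rate at unadjusted 0.05, all nulls true.** Independent tests: 1 − 0.95^k. Correlated tests: simulated equicorrelated normal statistics with |z| > 1.96. The correlations 0.5 and 0.8 are assumptions.

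| Family | k | Independent | Correlation 0.5 | Correlation 0.8 |
|---|---|---|---|---|
| Table 4 | 17 | 58% | 39% | 21% |
| Table 5 | 5 | 23% | 18% | 13% |

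For one predictor against the three outcomes, with Table 2's outcome correlations (0.79, 0.66, 0.65), the rate is 11%.

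Many nulls in Table 4 are plainly false. Setting aside its six strongest rows (sedatives three times, sleep difficulty once, sleep-related worry twice) leaves 11 tests. The rate is then 1 − 0.95^11 = 43% if independent, and 35% with Table 2's outcome correlations and predictors assumed independent.

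**4. The six results with p from 0.017 to 0.049.**

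*Table 4 (17 tests; six smaller p-values rank ahead).*
- Cost for PHQ-9, p = 0.028, rank 7: Holm 0.028 × 11 = 0.308; Hochberg 0.308; Benjamini-Hochberg 0.028 × 17/7 = 0.068.
- Sleep satisfaction for PHQ-9, p = 0.045, rank 8: Holm 0.045 × 10 = 0.45; Hochberg 0.441; Benjamini-Hochberg 0.045 × 17/8 = 0.096.

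Both fail all three procedures.

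*Table 5 (5 tests): stress 0.017, support 0.021, stage 0.049.*
- Holm: 0.017 × 3 = 0.051, which carries forward, so 0.051 for each.
- Hochberg: 0.042, 0.042, 0.049.
- Benjamini-Hochberg: 0.026, 0.026, 0.049.

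They miss Holm by 0.001 and pass the other two.

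*Cost and PHQ-9, Spearman, p = 0.017.* At N = 500 the other two cost correlations (−0.12 and −0.10) give p of about 0.007 and 0.025. Over the 9 printed tests the six sleep correlations rank first, so Holm gives 0.017 × 2 = 0.034 and the result passes. Section 2-6 also plans Spearman tests for number of children, which Table 2 does not print. With those three added, and if their p-values are larger than 0.025, Holm gives 0.017 × 5 = 0.085.

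**5. Table 5 has problems that adjustment cannot fix.**
- Support: OR 0.54, p = 0.021 in Table 5; coefficient −0.18, p = 0.606 in Table 6, labelled the corrected model.
- Stage: OR 0.61 in Table 5; coefficient +0.92 (p = 0.0014) in Table 6, the opposite direction.
- Stress: OR 1.14, CI 1.03 to 1.35. SE = (ln 1.35 − ln 1.03)/3.92 = 0.069; z = ln 1.14/0.069 = 1.90; p is about 0.058, against the printed 0.017. The interval's geometric midpoint is 1.18, and that value would give p of about 0.017. The odds ratio and its interval therefore do not fit together on the Wald scale. Stress is absent from Table 6.

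**6. What is unaffected.** Over 31 tests (Tables 3 to 6, the ROC and the cost-PHQ-9 correlation), Holm leaves the sedative, sleep difficulty, PHQ-9 and anger results below 0.05. Stage also stays below: the largest Table 3 value becomes 0.038 and Table 6's becomes 0.028.

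**The case against.** The strongest reply is that this is an observational study of correlations, already analysed, and its main findings do not depend on adjustment. Families defined after seeing the data cannot restore confirmatory error control, so labelling the associations exploratory is a legitimate alternative. That stands, and the fix adopts it. The label is nevertheless absent for everything except the path model, and elsewhere the text speaks of findings as confirmed.

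The rates in step 3 assume every null is true, which is not credible here. This also stands, but the 11 remaining tests in Table 4 still give about 35%.

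The Results text on Table 4 names only sedatives and sleep-related worry as significant. The cost and sleep-satisfaction rows fall below 0.05 under the blanket rule, but that text does not claim them.

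A reader might infer that all six results count as significant only because no correction was made. The documents do not support that. Table 5's rows pass two of three procedures within their own table, and the cost correlation passes Holm over the printed tests. For support and stage the larger difficulty is the conflict with Table 6. Calling stage non-significant after adjustment would present a sign reversal as chance.

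**Conclusion.** The point holds as a reporting and interpretation defect that should be corrected. No primary outcome or contrast is named, alpha is unadjusted, and the family-wise rate under the global null is several times 5%: for Table 4, 39% at an assumed correlation of 0.5, with a range of 21% to 58%. Only the two Table 4 results fail every procedure tried. The other four depend on the family and procedure, and Table 5's p-values should not be adjusted until that table is reconciled. A reader might go further and doubt the main associations. The printed p-values do not support that, because those associations survive Holm even over 31 tests.

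Cost needs particular care. Its crude correlation with PHQ-9 is negative (−0.11), while its adjusted coefficient in Table 4 is positive (7.5E-5).

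**What to change.** - **Section 2-6.** Replace the blanket rule with a statement that no primary outcome or contrast was specified, that the associations are exploratory, and that p-values are not error-controlled across analyses.
- **Table 4.** Print Holm-adjusted p-values over the 17 tests beside the raw ones, and state that this family was set after the data were seen.
- **Results and Discussion.** Call the six results exploratory, and do not describe them as established predictors or protective factors. Word the interpretation of treatment cost as hypothesis-generating.
- **Table 5, before any adjustment.** Reconcile it with Table 6 on support and on the direction of stage, check the stress odds ratio against its interval and p-value, and report a single retained logistic model. Remove the statement that Table 6 confirms Table 5.

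The Table 4 adjustment needs a few minutes with existing p-values and no new data. Reconciling the logistic models means returning to the dataset and the stage coding. The downside is that a few weak associations lose the word significant.

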### 3 - Results

A total of 500 breast cancer patients were included in the final analysis. Descriptive statistics revealed a high prevalence of psychological distress within the sample, with elevated scores in depression, anxiety, and stress domains.

Spearman correlation analysis revealed strong positive associations between sleep difficulty and psychological outcomes: depression ( $r = 0.85$ ), anxiety ( $r = 0.77$ ), and stress ( $r = 0.85$ ), all statistically significant at  $p < 0.001$ . Use of sedatives was also significantly correlated with elevated distress scores ( $r > 0.90$  across models).

Kruskal-Wallis tests demonstrated statistically significant differences in mean ranks of depression, anxiety, and stress across cancer stages ( $p < 0.01$ ), with higher distress in patients with advanced-stage disease.

Multivariate linear regression identified the following as significant predictors of psychological distress:

- PHQ9\_Total:  $\beta = 0.42$ ,  $p < 0.001$
- Anger:  $\beta = 2.08$ ,  $p < 0.001$
- Cancer Stage:  $\beta = 0.92$ ,  $p = 0.0014$

Psychological support was not a significant predictor ( $p = 0.606$ ).

Binary logistic regression showed that PHQ9 and anger significantly predicted severe anxiety, with odds ratios of 1.32 and 1.27, respectively ( $p < 0.001$ ). Stage of disease also emerged as a significant factor in anxiety prediction.

Receiver Operating Characteristic (ROC) curve analysis yielded an Area Under the Curve (AUC) of 0.74 for stress in predicting severe anxiety, indicating a fair level of discriminative ability.

Finally, conceptual path analysis demonstrated that the relationship between stress and anxiety was primarily indirect, mediated through sleep disturbance and daily performance impairment. The direct path from stress to anxiety was negligible ( $r = -0.01$ ), suggesting a mediated mechanism of action.

**Table 1.** Descriptive Statistics of Study Variables

Variable	N	Minimum	Maximum	Mean	SD
Total Cost	500	80	34785	3721.69	4456.79
PHQ9_Total	500	1	27	17.99	6.11
GAD7_Total	500	1	21	12.79	3.81
Cancer Stage	500	0	4	2.52	1.09
Children	500	0	5	2.53	1.63
Metastatic	500	0	1	0.36	0.48
Stress Level	500	0	4	2.64	0.79

The descriptive characteristics of the study variables are presented in **Table 1**. Depression and anxiety scores were moderately high, while stress levels were also elevated. Treatment cost showed substantial variability across participants.

**Table 2.** Spearman Correlation Matrix Among Study Variables

Variable	PHQ9_Total	GAD7_Total	Stress Level	Sleep Difficulty	Sleep Satisfaction	Total Cost

PHQ9_Total	1.00	0.79	0.66	0.85	0.49	-0.11
GAD7_Total	0.79	1.00	0.65	0.77	0.62	-0.10
Stress Level	0.66	0.65	1.00	0.85	0.55	-0.12
Sleep Difficulty	0.85	0.77	0.85	1.00	0.48	-0.08
Sleep Satisfaction	0.49	0.62	0.55	0.48	1.00	-0.09
Total Cost	-0.11	-0.10	-0.12	-0.08	-0.09	1.00

[figure not shown]
Spearman correlation coefficients between psychological outcomes and sleep-related variables are shown in **Table 2**. Strong positive correlations were observed between depression, anxiety, stress, and sleep difficulty.

**Table 3.** Kruskal–Wallis Test for Differences Across Cancer Stages

Variable	Chi-square (H)	df	P-value
Stress Level	31.092	3	<0.001
PHQ9_Total	14.762	3	0.002
GAD7_Total	19.705	3	<0.001

The Kruskal–Wallis test results (**Table 3**) indicate significant differences in depression, anxiety, and stress levels across cancer stages ( $P < 0.05$ ).

**Figure 1.** Chi-square (H) Values for Stress, Depression, and Anxiety

**Figure 1** shows the Chi-square (H) values for stress, depression, and anxiety. Stress exhibited the highest value (H = 31.09), followed by anxiety (H = 19.71) and depression (H = 14.76), all indicating significant differences across groups ( $P < 0.05$ ).

**Table 4.** Multiple Regression Analysis of Factors Associated with Depression, Anxiety, and Stress among Patients

Outcome	Predictor	B	T	P-value	VIF	R 
Depression (PHQ-9)	Use of Sedatives	4.842	10.817	<0.001	1.766	0.702
	Sleep Difficulty	4.52	11.221	<0.001	4.866	
	Sleep Satisfaction	0.364	2.01	0.045	1.021	
	Children	0.075	0.626	0.532	1.039	
	Total Cost	7.5E-5	2.209	0.028	1.022	

	Metastatic	-0.13	-0.408	0.684	1.048	
Anxiety (GAD7)	Use of Sedatives	4.064	12.807	<0.001	1.766	0.615
	Sleep-related Worry	1.521	6.193	<0.001	3.655	
	Sleep Satisfaction	0.539	1.886	0.060	4.866	
	Children	0.205	1.889	0.060	1.039	
	Total Cost	3.0E-5	1.246	0.213	1.022	
	Metastatic	0.203	0.896	0.371	1.048	
Stress Level	Use of Sedatives	1.856	29.413	<0.001	1.766	—
	Sleep-related Worry	0.149	3.048	0.002	3.655	
	Children	0.037	1.705	0.089	1.039	
	Metastatic	0.084	1.865	0.063	1.048	
	Total Cost	3.4E-6	0.711	0.477	1.022	

The results of the multiple regression analysis are summarized in **Table 4**. Use of sedatives and sleep-related worry were significant predictors of stress, depression, and anxiety scores.

**Table 5:** Binary Logistic Regression – Predicting Severe Anxiety

Predictor	Odds Ratio (OR)	95% CI	P-value
Depression (PHQ-9)	1.32	1.18 – 1.56	<0.001

Anger	1.27	1.11 – 1.49	0.002
Stress Level	1.14	1.03 – 1.35	0.017
Psychological Support	0.54	0.33 – 0.91	0.021
Cancer Stage	0.61	0.33 – 0.87	0.049

[figure not shown]
Binary logistic regression (**Table 5**) showed that depression, anger, and stress significantly increased the odds of severe anxiety, while psychological support and advanced cancer stage were protective. The corrected model (**Table 6**) confirmed these associations.

**Table 6.** Logistic Regression Predicting Severe Anxiety (Corrected Model)

Predictor	Coef. ( $\beta$ )	Std. Error	z-value	p-value	95% CI (Lower – Upper)
PHQ9_Total	0.42	0.06	6.92	<0.001	0.30 – 0.53
Anger	2.08	0.48	4.36	<0.001	1.14 – 3.02
Psych Support	-0.18	0.34	-0.52	0.606	-0.84 – 0.49
Cancer Stage	0.92	0.29	3.20	0.0014	0.36 – 1.48

[figure not shown]
This table presents the corrected logistic regression model for predicting severe anxiety. PHQ9\_Total and anger were significant positive predictors, while psychological support did not show a significant protective effect in the adjusted model.

**Figure 2.** ROC Curve for stress predicting severe anxiety.

The ROC curve (**Figure 2**) illustrates the predictive value of stress scores for severe anxiety, with an AUC of 0.74 ( $p < 0.001$ ), indicating fair discriminative accuracy.

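### The reported correlation of r > 0.90 between sedative use and the distress scores cannot be reconciled with Tables 2 and 4

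*Combined protocol and SAP*

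**What the plan says.** Section 2-6 (Data Analysis) names one correlation coefficient: "Bivariate analyses included Spearman's correlation coefficient to evaluate associations between psychological outcomes" and continuous predictors. Section 3 (Results) opens with "A total of 500 breast cancer patients were included in the final analysis". It lists Spearman correlations for sleep difficulty and then adds "Use of sedatives was also significantly correlated with elevated distress scores", giving r > 0.90 across models. Sedative use is not a row of Table 2, where the largest off-diagonal entry is 0.85.

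Sedative use does appear in Table 4, titled "Multiple Regression Analysis of Factors Associated with Depression, Anxiety, and Stress among Patients". Its rows (B, t, p, VIF and, where printed, model R²) are:

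- PHQ-9: "Use of Sedatives 4.842 10.817 <0.001 1.766 0.702"
- GAD-7: "Use of Sedatives 4.064 12.807 <0.001 1.766 0.615"
- Stress: "Use of Sedatives 1.856 29.413 <0.001 1.766", with a dash in place of R²

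The document does not say how sedative use is coded.

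**The concern.** The largest correlation in the Results has no table behind it, and it exceeds what a table containing the same variable appears to allow. A single predictor cannot explain more variance than the whole model that includes it.

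At stake is the size of the effect. A value above 0.90 tells a reader that sedative use is almost interchangeable with the distress scores. The Discussion, Clinical Implications and Conclusion all carry sedative use forward as a main correlate of distress, although none of them repeats the figure.

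**Working it through.** **Inputs.** Table 1: n = 500; SDs 6.11 (PHQ-9), 3.81 (GAD-7), 0.79 (stress), 4456.79 (Total Cost), 0.48 (Metastatic), 1.63 (Children). Table 2 (Spearman): PHQ-9 with GAD-7 0.79, PHQ-9 with stress 0.66, GAD-7 with stress 0.65. Table 4: the rows quoted above, with six predictors in the PHQ-9 and GAD-7 models and five in the stress model.

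**1. Trying to reproduce r > 0.90.** Nothing printed yields it.
- Multiple R of the full models: √0.702 = 0.838 and √0.615 = 0.784.
- If the printed R² values are adjusted ones, unadjusted R² = 1 − (1 − R²) × 493/499, and the roots are 0.840 and 0.787.
- Partial r = t/√(t² + df): 0.438 (PHQ-9), 0.500 (GAD-7), 0.798 (stress).

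**2. Pearson reading.** R² is at least the squared Pearson r of any one predictor, so |r| ≤ 0.838 (PHQ-9) and 0.784 (GAD-7). The bound tightens if the unique share of another predictor, t²(1 − R²)/df, is removed:
- PHQ-9, Sleep Difficulty: 11.221² × 0.298/493 = 0.076, so |r| ≤ √(0.702 − 0.076) = 0.79.
- GAD-7, Sleep-related Worry: 6.193² × 0.385/493 = 0.030, so |r| ≤ √(0.615 − 0.030) = 0.76.

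An r of 0.90 needs R² of at least 0.81.

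**3. Are the printed R² values credible?** Residual variance from R² is SD²(1 − R²) × 499/493. The same quantity follows from another row as (B/t)² × 499 × SD(x)²/VIF.

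| Source | PHQ-9 | GAD-7 | Stress |
|---|---|---|---|
| Printed R² | 11.26 | 5.66 | not printed |
| Metastatic row | 11.14 | 5.63 | 0.223 |
| Total Cost row | 11.18 | 5.62 | 0.222 |
| Children row | 18.3 | 15.0 | 0.60 |

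Two rows agree with the printed R² values. The Children row does not; its GAD-7 value exceeds the total variance of 3.81² = 14.5.

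**4. Spearman reading, no assumption about coding.** Rank correlations also form a correlation matrix, so r′R⁻¹r ≤ 1, where R is the Table 2 matrix for PHQ-9, GAD-7 and stress. The entries of R⁻¹ sum to 1.2555. With r = 0.90 for all three outcomes the form is 0.81 × 1.2555 = 1.017, above 1. The largest common value is 1/√1.2555 = 0.892. At the upper rounding limits (0.795, 0.665, 0.655) the form is 1.013 and the ceiling 0.894.

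**5. Spearman reading, sedative use coded 0/1 (assumption).** SD(x) = √(s² × VIF/(499 × SE²)), with SE = B/t and s² from the first table row.
- PHQ-9: SE = 4.842/10.817 = 0.4476, SD(x) = 0.446.
- GAD-7: SE = 4.064/12.807 = 0.3173, SD(x) = 0.446.

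The variance of 0.199 equals p(1 − p) at p of about 0.27 or 0.73. The Spearman ceiling against an essentially untied score is √(3 × 0.199) = 0.77. With normal-shaped integer scores given the Table 1 means, SDs and ranges, it stays at 0.77 to 0.78 for PHQ-9 and GAD-7. An even split would give 0.866.

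**6. Stress.** The ceiling in step 5 does not carry over to a 0–4 score with many ties. For example, take sedative use split 137/363 and stress counts of 30, 0, 100, 362 and 8 at levels 0 to 4. The stress mean is 2.64 and the SD 0.79, as in Table 1. With all 137 non-users lowest, Pearson r is 0.796 and Spearman r is 0.94.

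**The case against.** The strongest reply is that the sentence follows Spearman results and Spearman is the planned coefficient, so an R² from a linear model does not bound it. That is correct as far as it goes, and it is why step 4 is needed. Step 4 has limits of its own. Its margin is narrow (0.892 to 0.894 against 0.90), and it excludes only the claim for all three outcomes together. For PHQ-9 and GAD-7 as a pair, the Table 2 ceiling is √((1 + 0.79)/2) = 0.946. To rule out a Spearman value above 0.90 for those two scores separately, one needs the inferred 0/1 coding.

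A reader might infer that the 0.77 ceiling applies to all three outcomes. It does not: the stress example reaches 0.94 within the Table 1 figures. A stress R² of about 0.65 can be back-solved, but only by borrowing other rows or the sedative variance from the other models. It also implies a standardised coefficient of about 1.05, so it is not a secure bound.

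A second objection is that Table 4 is not clean. The Children rows fail step 3, and Sleep Satisfaction has a VIF of 1.021 in one model and 4.866 in another. This stands as a caution, although the entries used in steps 2 and 5 agree with two independent rows. A figure next to Table 2 is not shown in the text available, so its content could not be checked.

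**Conclusion.** The point holds as an unreconciled inconsistency: r > 0.90 across models and the study's tables cannot all be right. On a Pearson reading it fails for PHQ-9 (at most 0.84, about 0.79 when tightened) and GAD-7 (at most 0.78, about 0.76 when tightened). On a Spearman reading it fails as a statement about all three outcomes (at most about 0.89). If sedative use is 0/1, it also fails for PHQ-9 and GAD-7 individually (at most about 0.77). It is not excluded for stress alone. The conclusion assumes that the statement covers PHQ-9, GAD-7 and stress, and that the relevant Table 2 and Table 4 entries are correctly printed.

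Two stronger inferences are tempting and unsupported. One is that r > 0.90 is proven to be the faulty number. The agreement in step 3 and the separate conflict with Table 2 point that way, but only the data can settle it. The other is that the link between sedative use and distress falls. It does not: the sedative t values in Table 4 run from 10.8 to 29.4, and the later sections make only qualitative claims, which a correlation of about 0.75 would still support.

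**What to change.** Recompute the correlation of sedative use with PHQ-9, GAD-7 and stress from the data, and report one value per outcome. State the coefficient type and how sedative use is coded. Add sedative use to Table 2 and print the missing stress R² in Table 4. Check the Children rows and the Sleep Satisfaction VIFs against the software output. Then replace r > 0.90 across models with the recomputed values, and keep the qualitative statement if they support it. If sedative use proves to be yes/no, it also falls outside the planned use of Spearman for continuous predictors; a group comparison would then be an option, but the correction does not depend on it.

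The cost is three recomputed coefficients, a check of one table's output and one rewritten sentence. No new data are needed. The stated effect size will probably fall.
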